### 10.7.2 Observation Arm

Patients who are randomized to the Observation Arm will attend the Initial Follow-up Visit 35 days ( $\pm$  5 days) after study treatment discontinuation criteria are met.

In the event the patient withdraws consent to any further study participation and refuses to attend the Initial Follow-up Visit, the following procedures and evaluations must be performed at the time the patient withdraws consent.

1. Record concomitant medications through 30 days after study treatment discontinuation criteria ([Section 11.1](#)) are met.
2. Record all AEs and attribution (see <http://ctep.cancer.gov/reporting/ctc.html>) through 30 days after study treatment discontinuation criteria ([Section 11.1](#)) are met.
3. Assess and record B symptoms.

4. Perform physical examination. Document any new or worsened findings as AEs.
5. Assess and record ECOG performance status (see [Appendix 3](#)).
6. Local laboratory: collect blood for hematology and serum chemistry (including LDH, see [Section 12.1](#))
7. Review dosing of folic acid and document compliance.
8. Instruct patient to discontinue folic acid and vitamin B12.
9. Record reason for discontinuation of observation ([Section 11.1](#)).
10. Record first subsequent therapy for PTCL, if applicable. First subsequent therapy for PTCL is at the investigator's discretion and can include pralatrexate.

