### 11.1 Criteria for Study Treatment Discontinuation

Patients will receive study treatment (pralatrexate or observation) until one of the following criteria for study treatment discontinuation applies:

- Development of PD
- Initiation of RT or systemic chemo/biological therapy for treatment of PTCL
- Receipt of systemic steroids > 10 days, with the exception of those as stated in exclusion criterion #5 (see [Section 8.4](#))
- Development of an AE that interferes with the patient's participation
- Lost to follow-up
- Patient decision
- Investigator decision
- Sponsor decision

In addition, for those patients randomized to the Pralatrexate Arm, additional pralatrexate treatment discontinuation criteria are:

- 3 or more consecutive doses of pralatrexate omitted or more than 28 days between doses of pralatrexate
- Treatment with pralatrexate for 2 years

Patients will be seen for the Initial Follow-up Visits as outlined in [Section 10.7](#).

If an investigator feels that a patient would continue to benefit from pralatrexate therapy after completion of 2 years' therapy, they should discuss with the sponsor's medical contact and agree whether or not it is appropriate to continue treatment.

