### **13.9 Radiotherapy, Cytotoxic Therapy, Biologic Therapy, or Immune Response Modifiers**

No RT, other cytotoxic agents, biologic therapy, immune response modifiers, or stem cell transplant are to be administered to patients until pralatrexate/observation has been discontinued.

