### 14.3 Recording of Adverse Events

#### 14.3.1 Recording of Adverse Events

Any AE that occurs from the time the study IC is obtained until randomization needs to be recorded on the AE CRF page(s), **only** if the event was related to a study procedure. All other AEs/findings prior to randomization must be recorded as baseline findings on the applicable CRF page(s).

Any AE that occurs from randomization through 30 days after the last dose of pralatrexate or through 30 days after treatment discontinuation criteria are met for the Observation Arm must be recorded on the AE CRF. From 31 days after the last dose of pralatrexate, only AEs that are related to pralatrexate need to be captured on the AE CRF.

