## Appendix 2 Schedule of Study Procedures/Evaluations Table for Observation

Visit	SCREENING	BASELINE VISIT	SUBSEQUENT ASSESSMENTS		RESPONSE	FOLLOW-UP		
	Within 21 Days Prior to Randomization	Within 3 Days Following Randomization	Patient Contact Week 2 of 4-week Period	Clinic Visit Every 28 (± 3) Days	At 8 (± 1) Weeks Post Randomization, Every 12 (± 1) Weeks Thereafter 	Initial FU	Post-treatment FU/ Response Evaluation	Long-term FU
Informed consent  , Eligibility  , Medical/surgical history	X							
Confirmation of diagnosis by independent pathology review	X 							
B symptoms (> 38°C, night sweats, loss > 10% of body weight)	X	X		X				
IPI score	X 							
CHOP-based chemotherapy	X 							
CT scan (chest, neck, abdomen, pelvis)  ; Whole-body PET  ; Medical photography 	X				X		X	
Bone marrow biopsy/aspirate	X 				X 		X 	
ECG	X							
Physical examination	X				X	X	X	
ECOG Performance Status (see Appendix 3)	X					X		
Hematology  /Chemistry  /Serum β-hCG Pregnancy Test 	X	X 		X 		X		
Vitamin B 12 	X	X		X				
Folic acid 	X	X		X		X 		
Concomitant medications		X		X		X 		
Adverse events	X	X	X	X		X 		
Height and weight		X 						
Response assessment					X 		X 	
Reason for discontinuation of observation						X		
Subsequent therapy						X	X	X
Survival status								X

First response evaluation is 8 weeks (± 1 week) after randomization; see Section 10.6 for timing of response. Can be obtained prior to the screening period in order for confirmation of pathology prior to randomization. Document IPI score at initial diagnosis. Document dates, best response and post-CHOP response. Sections 10.1 and 10.6. Section 10.1. Section 10.6. Section 12.1. For females who are not postmenopausal or surgically sterile; perform within 14 days prior to randomization. Section 10.5. Section 7.1. Until treatment discontinuation criteria are met for patients in the Observation Arm. Tumor biopsy may be performed, if needed to confirm response, per investigator decision.

---

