PFS time is calculated as the number of days from randomization to the date of objective documentation of PD or death, regardless of cause (PD date/death date - date of randomization + 1). Patients who are alive without a disease response assessment of PD will be censored at their last disease assessment date or the date of randomization, whichever is later. Date of progression will not be imputed for patients with missing tumor assessment(s) before an assessment of PD. Patients who withdraw from treatment prior to PD without withdrawing consent will be followed for disease status whenever possible, even if subsequent therapy, including transplant, has been initiated prior to documented PD per central review at least until the first interim analysis. Patients who have not died and who have no response assessments after baseline will be censored at randomization.

Overall Survival Time

OS time is calculated as the number of days from randomization to death (date of death - date of randomization + 1). Patients who have not died (no record of death) or are lost to follow-up will be censored at the date of last contact. Patients who withdraw from study visit participation will be followed for survival status. OS will be reported in months.

Treatment-emergent Adverse Event

A treatment-emergent AE is defined as an AE that occurs on or after study day 1 and that is a higher grade than was present just prior to study day 1.

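### Treatment-emergent AEs have no end at subsequent PTCL therapy, so early rescue toxicity, including that of crossover pralatrexate, can be tabulated under Observation

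*SAP*

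**What the plan says.** **Definition.** SAP 5.2: "A treatment-emergent AE is defined as an AE that occurs on or after study day 1 and that is a higher grade" than the patient had just before study day 1. No end date and no link to subsequent therapy follow. SAP Table 9.1 restricts every AE table to events meeting this definition, and SAP 8.6 tabulates them by treatment group.

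**Collection, Observation Arm.** Under Protocol 14.3.1, any AE from randomization "through 30 days after treatment discontinuation criteria are met for the Observation Arm must be recorded on the AE CRF". Protocol 10.7.2 gives the same limit, and 14.6.2 gives it for SAEs.

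**What starts the clock.** The criteria in Protocol 11.1 include PD and "Initiation of RT or systemic chemo/biological therapy for treatment of PTCL". Protocol 13.9 adds that no radiotherapy, cytotoxic, biologic or immune-modifying treatment or "stem cell transplant are to be administered to patients until pralatrexate/observation has been discontinued".

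**What rescue may be.** Protocol 10.7.2: "First subsequent therapy for PTCL is at the investigator's discretion and can include pralatrexate". Relatedness is scored against pralatrexate (Protocol 14.5).

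**Collection, Pralatrexate Arm.** All AEs are recorded to 30 days after the last dose. Protocol 14.3.1 then says: "From 31 days after the last dose of pralatrexate, only AEs that are related to pralatrexate need to be captured on the AE CRF".

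**Conflicting stops.** In Protocol Appendix 2, footnote 12 qualifies the Observation Arm's AE entry at the Initial Follow-up Visit with "Until treatment discontinuation criteria are met for patients in the Observation Arm", which leaves no 30-day tail. Protocol 10.8 asks for study-treatment-related AEs at each follow-up visit in all randomized patients, but Appendix 2 has no AE entry at post-treatment follow-up.

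**The concern.** Safety of pralatrexate is the study's only secondary objective, and the Observation Arm supplies the background against which its AE rates are read. That arm is otherwise untreated apart from vitamins. The 30 days after PD, or after new therapy starts, are when cytotoxic rescue can begin. Under the SAP as written, a mucositis on crossover pralatrexate in that window is a treatment-emergent AE of Observation and, if scored related, a treatment-related one. The test drug's own toxicity would then be counted in its comparator.

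SAP 8.5.2 recognises crossover as a confounder of OS, and 8.5.5 offers a sensitivity analysis for it. The safety section has no counterpart. SAP 11.3 defines a variable for the interval from treatment stop to AE start and says it serves for post-treatment cutoffs. It names no cutoff, does not refer to subsequent therapy, and does not say what the stop day is for a patient under observation.

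**Working it through.** The documents state no AE rate or safety contrast, so there is no plan figure to reproduce. The check is a trace of the rules, followed by two calculations of scale.

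**1. Trace**
- *Observation, PD first.* PD meets a criterion and the 30-day window opens. If rescue starts d days later (d < 30), then 30 − d days of collection fall on rescue.
- *Observation, new therapy is the criterion.* The window opens when therapy starts, so all 30 days fall on rescue.
- *Pralatrexate.* The window opens at the last dose. Rescue begun inside it is also collected as all-cause. If dosing stopped earlier, for an AE, omitted doses or the 2-year limit, the all-cause window may close before rescue starts.
- *Before discontinuation.* Protocol 13.9 bars rescue in either arm, so only the tail is exposed.

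Neither the definition nor collection stops at rescue, but collection limits the all-cause leak to 30 days.

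**2. Share of Observation Arm collection time in the tail**

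Inputs: 10-month median PFS, exponential (SAP 3.2); observation for at most 24 months (SAP 3); tail of 30/30.4375 = 0.99 month.
- λ = ln 2 / 10 = 0.0693 per month
- P(PFS event by 24 months) = 1 − exp(−24 × 0.0693) = 0.81
- Mean time to event or 24 months = 0.81 / 0.0693 = 11.7 months
- Tail share, all patients: 0.99 / (11.7 + 0.99) = 7.8%
- Tail share, only patients with an event: 0.81 × 7.8% = 6.3%

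The tables count patients with an event, not person-time, so 6% to 8% does not cap the effect on incidence.

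**3. Illustration on incidence (AE inputs are assumptions, not in the documents)**

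Assume true Grade 3+ incidence p of 15% under Observation and 55% under Pralatrexate. Let f be the share starting rescue inside the window (0.2 to 0.8) and g the chance of a new Grade 3+ AE there (0.2 to 0.6). The leak is L = P(event by 24 months) × f × g, and tabulated incidence is p + (1 − p) × L. For Pralatrexate, with HR 0.67, P = 1 − exp(−24 × 0.0693 × 0.67) = 0.67.

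| f, g | Observation | Pralatrexate | Difference, both arms leak | Difference, only Observation leaks |
|---|---|---|---|---|
| none | 15% | 55% | 40 points | 40 points |
| 0.2, 0.2 | 0.15 + 0.85 × 0.032 = 18% | 0.55 + 0.45 × 0.027 = 56% | 38 points | 37 points |
| 0.8, 0.6 | 0.15 + 0.85 × 0.389 = 48% | 0.55 + 0.45 × 0.323 = 70% | 21 points | 7 points |

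The added Observation patients number about 5 to 61 of 183. The risk ratio moves from 3.7 to between 3.2 and 1.4 with leakage in both arms. The contrast shrinks in every row, but the width of the range comes from the assumed inputs.

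**The case against.** The case against giving this much weight is substantial.

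- *The leak is bounded.* A reader might infer from the open-ended definition that rescue toxicity accumulates without limit. Protocol 14.3.1 does not support that: all-cause collection stops 30 days after criteria are met, and there is no tail at all if Appendix 2 footnote 12 governs. A longer leak needs Protocol 10.8 to be read as covering crossover pralatrexate, and its text is ambiguous. This objection stands.
- *The other arm leaks too.* A reader might infer that contamination is heavier under Observation because its clock starts at PD or new therapy rather than at last dose. That is plausible but not shown. With dosing in 3 of every 4 weeks, a patient who progresses on treatment has usually been dosed recently. Related AEs in the Pralatrexate Arm are also captured beyond day 30, although those are genuine drug effects and do not cancel contamination of the comparator.
- *A patient count is tempting.* At month 45 the plan's assumptions give about 283 PFS events, about 106 of them among 549 × 45/54 × 1/3 ≈ 152 Observation patients. If 50–80% start rescue within 30 days and 30–60% of those have a Grade 3+ AE, the result is 16 to 51 patients, or 10–33%. The documents do not support this. Both rates are assumed, and PFS events include deaths. Only about 99 of the 106 fall within the 2-year observation limit. Patients who already had a Grade 3+ AE add nothing to an incidence table, and not every AE after progression is caused by rescue.
- *Some protection exists.* Toxicity of rescue other than pralatrexate should be scored unrelated, so only crossover can reach the treatment-related tables. Subsequent-therapy timing and AE listings are planned, so cases could be traced afterwards. This does not correct the main tables.
- *Nothing confirmatory depends on it.* AE summaries are descriptive; no primary endpoint or stopping boundary is affected. This limits the priority.

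**Conclusion.** The gap is real and modest. The SAP gives treatment-emergent AEs no end and no cut at subsequent PTCL therapy. Where the 30-day rule in Protocol 10.7.2 and 14.3.1 is followed, early rescue toxicity can be tabulated under Observation, and crossover pralatrexate toxicity can appear there as treatment-related. The likely direction is a higher background rate and a smaller all-cause contrast. The exposed tail is about 6% to 8% of Observation Arm collection time, given exponential PFS with a 10-month median and a 24-month limit. The effect on incidence is not determined by the documents, and the figures in the illustration rest on assumed AE and rescue rates. The contradiction over when Observation Arm collection stops is firm and must be reconciled whatever the size of the leak.

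**What to change.** In SAP 5.2 and 8.6:

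1. End the all-cause treatment-emergent period in both arms at the earlier of (a) 30 days after the last dose (Pralatrexate Arm) or after discontinuation criteria are met (Observation Arm), and (b) the day before first subsequent PTCL therapy, whether systemic, RT or transplant.
2. Keep pralatrexate-related AEs of the Pralatrexate Arm in the main tables whenever they start. Protocol 14.3.1 collects them deliberately after day 30, and a plain cut would hide delayed drug toxicity.
3. Show AEs that start after subsequent therapy in a separate table by arm. Present those on crossover pralatrexate on their own, and do not count them as treatment-related under Observation.

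In the Protocol, reconcile the Observation Arm's AE collection stop across 10.7.2, 10.8, 14.3.1 and Appendix 2 footnote 12.

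The cost is wording and one extra table. SAP Table 9.1 already plans to summarise the timing of subsequent therapy. The downside is that some late all-cause AEs, including delayed drug effects not scored as related, move out of the main table.

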6 ANALYSIS SUBSETS

6.1 Primary Analysis Set

The primary efficacy set, also referred to as the intent-to-treat population or full analysis set (FAS), will include all randomized patients. Each patient will be included in the treatment group assigned at randomization, regardless of the treatment received. This analysis set will be used for the primary analyses of all efficacy endpoints.

6.2 Safety Analysis Set

The safety analysis set consists of all patients randomized to the Pralatrexate Arm who receive at least 1 dose of pralatrexate plus all patients randomized to the Observation Arm who do not discontinue study within 3 days of randomization. This analysis set will be used for the primary analyses of all safety endpoints.

6.3 Interim Analysis Set

There are 2 formal interim analyses planned for this study: 1 after both 280 PFS events and 128 OS events have occurred and 1 after 256 OS events have occurred. The interim analysis set will include all randomized patients who have at least 8 weeks of follow-up (ie, those who have reached the first scheduled response assessment) or who have discontinued the study prior to the first scheduled response assessment. This analysis set will only be used in the analysis of objective response rate (ORR).

6.4 Subgroup Analyses

The summaries of the primary and secondary efficacy variables and the comparisons of the treatment groups will be performed for subgroups defined by the covariates identified in [Section 4.4](#).

Summaries of treatment-emergent AEs will be provided for subgroups defined by age (< 65 vs \geq 65), gender, and race (if feasible).

7 DATA SCREENING AND ACCEPTANCE

7.1 General Principles

The case report tabulations (CRTs) will be built for this study. Data will be reviewed and cleaned prior to the creation of the final CRTs for this study.

7.2 Handling of Missing and Incomplete Data

Missing and incomplete data will be identified through a review of tables and listings for this study. Missing and incomplete data will be identified for investigation, and possible resolution, by Allos Data Management prior to the study database lock.

In general, missing data will be treated as missing, unless otherwise specified. Missing and incomplete dates for AEs, concomitant medications, and historical data will be imputed within this study based on the conventions described in [Section 11.3](#). Any AE with no stop date will be considered ongoing.

7.3 Testing/Validation Plan

SAS[®] Version 8.2 or higher on the Windows[®] system will be used for all CRT and tables, listings, and graphs (TLGs) creation.¹² Departmental standard macros will be used whenever appropriate for the creation of these items. These macros, as well as SAS[®], have already passed a rigorous validation process and further validation will not take place, although outputs will be verified. The verification of all outputs, as well as the review of all programs and macros created specifically for this study, will be conducted as outlined in Allos Standard Operating Procedures.

8 STATISTICAL METHODS OF ANALYSIS

8.1 General Principles

Unless otherwise indicated, analyses will be performed on the FAS.

8.2 Patient Accountability

The number of patients randomized (FAS) and in the safety analysis set will be summarized by treatment group and stratum. The reason for treatment discontinuation and study discontinuation will be summarized.

The number of patients included in each analysis set will be presented.

8.3 Important Protocol Deviations

The incidence of important protocol deviations (IPDs) will be summarized for each treatment group based on the IPDs identified within the database by the clinical study team. These specific IPDs will be detailed in a separate document.

8.4 Demographic and Baseline Characteristics

Demographics (age, gender, race, geriatric age group [< 65 years old vs ≥ 65 years old]) and other baseline disease characteristics including Eastern Cooperative Oncology Group (ECOG) performance status, IPI, and histopathology will be summarized using descriptive statistics for the FAS.

8.5 Efficacy Endpoints

8.5.1 Progression-free Survival

The stratified log-rank test will be the primary method used to test the hypothesis that pralatrexate extends PFS relative to observation. In addition, the stratified Cox regression model will be used to calculate the PFS HR, along with the 95% CI. Strata used in these analyses will be those used for study randomization (as recorded using the interactive response technology [IRT]). Results of the unstratified Cox regression model (and log-rank test) will also be presented. The proportional hazards assumption of the Cox model will be assessed.

8.5.2 Overall Survival

The stratified log-rank test will be the primary method used to test the hypothesis that pralatrexate extends OS relative to observation. In addition, the stratified Cox regression model will be used to calculate the OS HR, along with the 95% CI. Strata used in these analyses will be those used for study randomization (as recorded using the IRT). Results of the unstratified Cox regression model (and log-rank test) will also be presented. The proportional hazards assumption of the Cox model will be assessed.

It is recognized a priori that pralatrexate may be administered to Observation Arm patients subsequent to meeting treatment discontinuation criteria and thus, interpretability of the effect on OS may be confounded by crossover.

8.5.3 Objective Response Rate

The number and percentage of patients with an objective response of CR or PR, relative to disease status at the time of study entry, will be summarized by treatment group. The percentage will be calculated by dividing the number of patients within each category of response by the number of patients with measurable disease at baseline. Each patient will be counted within only 1 response group, with the overall best response during the study as the classification group. The treatment groups will be compared with respect to objective response rate (PR + CR) using the stratified Cochran-Mantel-Haenszel test. A 2-sided 95% exact CI will be calculated for the difference in objective response rates between the 2 treatment groups. Descriptive statistics will be provided for overall best tumor response for each treatment group.

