## 10.8 Follow-up Visits

All patients who are randomized are to have follow-up as outlined below until objectively documented PD; thereafter, patients are followed for survival. The timing of follow-up will be at 8 weeks ( $\pm 1$  week), then every 12 weeks ( $\pm 1$  week) through 3 years post-randomization, and then every 24 weeks ( $\pm 4$  weeks) thereafter through 7 years post-randomization. PD will be confirmed by central review until the first PFS analysis, see [Section 15.6.1](#), and per investigator assessment thereafter.

The following procedures/evaluations must be performed at each follow-up time point.

1. Record study-treatment-related AEs (see <http://ctep.cancer.gov/reporting/ctc.html>).
2. Evaluation of response (see [Section 10.6](#) for tests and procedures).
3. Record subsequent therapies for PTCL and document the best response to the first subsequent therapy.

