## 15.7 Efficacy Endpoints

### 15.7.1 Progression-free Survival

PFS time is calculated as the number of days from randomization to the date of objective documentation of PD or death, regardless of cause (date of PD or death - date of randomization + 1). Patients who are alive without a disease response assessment of PD will be censored at their last disease assessment date or the date of randomization whichever is later. Date of progression will not be imputed for patients with missing tumor assessment(s) before an assessment of PD. Patients who withdraw from treatment prior to PD without withdrawing consent will be followed for disease status whenever possible, even if subsequent therapy, including transplant, has been initiated prior to documented PD per central review at least until the PFS analysis. Patients who have no response assessments after baseline will be censored at randomization.

Strata used in the analyses will be those used for study randomization (as recorded on the IRT). With this technique, the HR can be consistently estimated (assuming the proportional hazards model is correct), as the potential bias due to the asymmetric visits is removed. It also corrects for the Type I error inflation and retains the nominal study power.

The primary analysis of PFS will be based on PD as determined by independent central review blinded to treatment group assignment. A separate charter will detail specifics about central review operation and response/PD definition details. Additional analyses will use the investigators' assessment of response.

The stratified log-rank test will be the primary method used to test the hypothesis that pralatrexate extends PFS relative to observation. In addition, the stratified Cox regression model will be used to calculate the PFS (HR), along with the 95% confidence interval (CI). Results of the unstratified Cox regression model (and log-rank test) will also be presented. The proportional hazards assumption of the Cox model will be assessed.

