### 15.7.3 Objective Response Rate

The number and percentage of patients with an objective response of CR or PR will be summarized. The percentage will be calculated by dividing the number of patients within each category of response by the number of patients with measurable disease at baseline. Each patient will be counted within only 1 response group, with the overall best response during the study as the classification group. The treatment groups will be compared with respect to objective response rate (CR + PR) using the stratified Cochran-Mantel-Haenszel test. A 2-sided 95% exact CI will be calculated for the difference in objective response rates between the 2 treatment groups. Descriptive statistics will be provided for best tumor response for each treatment group.

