4.2 Secondary Efficacy Endpoint

The secondary efficacy endpoint is objective response (CR or PR) to pralatrexate versus observation.

The primary analyses of PFS and objective response at the first interim analysis will use the central review of tumor assessments per International Workshop Criteria (IWC) without positron emission tomography (PET). Additional analyses of PFS and objective response will use IWC, including PET, and investigators' assessment of response. Additional details regarding central review will be provided in the reviewer's charter.

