5.2 Definitions

Screening Phase

The screening phase is the period between signing of informed consent and randomization.

Baseline

For efficacy assessments, baseline is defined as the last assessment prior to randomization. For safety assessments, baseline is defined as the last assessment prior to study day 1.

Study Day 1

Study day 1 is defined as the treatment start date. By convention, when known, assessments that occur on the same date as the treatment start date but that occur before treatment will be assigned as study day 0; those occurring in the same day but after treatment start will be assigned as study day 1. For patients randomized to the Observation Arm, study day 1 will be assigned to all patients who do not withdraw from the study prior to 3 days post-randomization, and will be equal to the randomization date plus 3 days.

Cycle

For patients randomized to the Pralatrexate Arm, a cycle will be calculated as the time from the first administration of pralatrexate for the given cycle to the day before the first administration of the subsequent cycle. The last cycle for a patient will be calculated as the time from the first administration of protocol-specified treatment for the given cycle plus 4 weeks or to the last dose administered within the cycle, whichever is longer.

Complete Response

CR is defined based on the IWC.¹¹ The same imaging method(s) used to document disease pre-randomization are to be used for post-randomization response assessments.

Partial Response

PR is defined based on the IWC.¹¹ The same imaging method(s) used to document disease pre-randomization are to be used for post-randomization response assessments.

Objective Response

Objective response is defined as a tumor response assessment of either CR or PR based on IWC.¹¹ The same imaging method(s) used to document disease during screening are to be used for subsequent response assessments.

Stable Disease

SD is defined using IWC.¹¹

Progressive Disease

PD is defined using IWC.¹¹

Progression-free Survival Time

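### Objective response has no cut-off at subsequent therapy, so responses to other PTCL treatment begun before documented PD are credited to the randomized arm

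*SAP*

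**What the plan says.** SAP 4.2 names the endpoint: "The secondary efficacy endpoint is objective response (CR or PR) to pralatrexate versus observation". SAP 5.2 defines the event without reference to the treatment being received: "Objective response is defined as a tumor response assessment of either CR or PR based on IWC".

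SAP 8.5.3 then sets the counting rule: "Each patient will be counted within only 1 response group, with the overall best response during the study as the classification group". Protocol 15.7.3 classifies patients in the same way, "with the overall best response during the study as the classification group". Both sections use patients with measurable disease at baseline as the denominator, and both plan a stratified Cochran-Mantel-Haenszel test and an exact confidence interval. Neither gives an end date for the assessments that count.

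Other provisions decide which assessments exist:

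- Protocol 10.6 continues response assessments until PD per central review, at least until the PFS analysis, and sends unscheduled assessments to the central reviewer too.
- Protocol 10.8: "All patients who are randomized are to have follow-up as outlined below until objectively documented PD". After that, patients are followed for survival.
- Protocol 15.7.1 follows disease status, where possible, in patients who leave treatment before PD, "even if subsequent therapy, including transplant, has been initiated prior to documented PD per central review". SAP 5.2 repeats this: "even if subsequent therapy, including transplant, has been initiated prior to documented PD per central review at least until the first interim analysis".
- Protocol 11.1 lists reasons for ending study treatment other than PD, including the start of other PTCL therapy, an adverse event, and patient or investigator decision.
- Protocol 10.7.2 leaves the first subsequent therapy of observation patients to the investigator's "discretion and can include pralatrexate".
- Protocol 10.8 and 10.9 record the best response to the first subsequent therapy as a separate item.

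**The concern.** Following patients through a change of therapy suits PFS, where the question is time to progression or death under the assigned strategy. It does not suit a response endpoint that is meant to describe what pralatrexate achieves relative to observation.

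Take an observation patient who enters in PR. The site calls PD, central review does not confirm it, and the patient leaves observation, receives pralatrexate and reaches CR. Scans are still being read centrally, so under the written rule this is a response on observation, although the study drug produced it. Equally, a pralatrexate patient who stops without PD and reaches CR only after a transplant is a pralatrexate responder.

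ORR is the only secondary efficacy endpoint and it has a formal test. Its denominator may be small, so a few such cases could visibly move the result and change what it means.

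**Working it through.** **Is there a cut-off anywhere?** The documents give no expected ORR, ORR power or ORR significance level, so there is no planned figure to reproduce. The check is first one of reading.

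1. *Counting window.* SAP 8.5.3 and Protocol 15.7.3 use the whole study. The SAP's added reference to disease status at study entry fixes the starting point, not the end.
2. *Event definition.* SAP 5.2 accepts any CR or PR assessment.
3. *Analysis set.* SAP 6.1 and Protocol 15.3.1 analyse patients as randomized. SAP 6.3 restricts the patients used for ORR at an interim analysis. Both say who is counted, not which assessments count.
4. *Are there assessments after new therapy?* Yes, if the therapy began before documented PD (Protocol 10.6 and 15.7.1, SAP 5.2).
5. *Can new therapy begin before documented PD?* Yes. Protocol 13.9 bars it only until pralatrexate or observation is discontinued, and Protocol 11.1 allows that for non-PD reasons. SAP 8.5.2 ties crossover to meeting the discontinuation criteria, not to PD alone.
6. *After documented PD?* Scheduled response assessment ends, and response to the first subsequent therapy is a separate item. These responses mostly stay out of the ORR data, although no sentence excludes them.

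**Illustration of size.** Every input marked A is an assumption.

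- Observation arm 183, pralatrexate arm 366 (SAP 3.2).
- About 50% CR and 10-20% PR after CHOP (SAP 3.2). PR share of responders = 10/60 to 20/70 = 16.7-28.6%.
- A: measurable disease at baseline means PR at entry. Observation: 183 × 0.167 to 183 × 0.286 = about 31-52. Pralatrexate: 366 × the same shares = about 61-105.
- One misattributed response moves the observation ORR by 1/52.3 to 1/30.5 = 1.9-3.3 points.

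Let p be the true ORR, f the share starting other therapy before central PD, and r the response rate to that therapy. Patients who have already responded cannot be added again, so

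observed ORR = p + (1 − p) × f × r.

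- A: observation p = 5-10% and f = 10-30%.
- A: r = 29-47%, borrowed from the PDX-008 pralatrexate response rates in Protocol 5.

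Smallest rise: 0.90 × 0.10 × 0.29 = 2.6 points. Largest: 0.95 × 0.30 × 0.47 = 13.4 points. The observation ORR becomes 0.05 + 0.95 × 0.029 = 7.8% at the lowest and 0.10 + 0.90 × 0.141 = 22.7% at the highest.

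**Both arms.** A: pralatrexate p = 29%, with r = 47% in both arms. Differences are in percentage points, computed before rounding.

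| f obs / f pral | Pral ORR | Obs ORR (p = 5%) | Difference (true 24.0) | Obs ORR (p = 10%) | Difference (true 19.0) |
|---|---|---|---|---|---|
| 0 / 10% | 32.3% | 5.0% | 27.3 | 10.0% | 22.3 |
| 10% / 10% | 32.3% | 9.5% | 22.9 | 14.2% | 18.1 |
| 30% / 10% | 32.3% | 18.4% | 13.9 | 22.7% | 9.6 |
| 30% / 30% | 39.0% | 18.4% | 20.6 | 22.7% | 16.3 |

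With equal r, the difference shrinks when (1 − p_obs) × f_obs exceeds (1 − p_pral) × f_pral, and grows otherwise. It grows once f_pral / f_obs exceeds 0.90/0.71 = 1.27 to 0.95/0.71 = 1.34. The sign is therefore not fixed.

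**The case against.** **Scope.** A reader might infer that every response to any later therapy over seven years of follow-up enters ORR. The documents do not support that. Response assessment ends at documented PD, response to the first subsequent therapy is recorded separately, and SAP 4.2 places the primary objective response analysis at the first interim analysis, by central review without PET. The route is narrowed further: planned PTCL treatment is an exclusion criterion, Protocol 13.9 bars other therapy while on study treatment, and follow-up after leaving treatment is only where possible. All of this stands, and it confines the problem to therapy begun before documented PD.

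**Estimand.** Efficacy is analysed as randomized, regardless of treatment received, so one could call the rule a treatment-policy ORR. But the analysis set does not define the response window, and the stated endpoint is response to pralatrexate versus observation. The SAP itself treats crossover as confounding for OS (8.5.2) and offers an optional sensitivity analysis for it (8.5.5). ORR has no counterpart.

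**The charter.** The central review charter is not among the documents and may specify eligible assessments. It cannot be assumed to do so, and a counting window for a tested endpoint belongs in the SAP.

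**Size.** A reader might take the rise in observation ORR as the bias in the comparison, and as running against pralatrexate. Neither follows. The share f is assumed, r comes from relapsed or refractory patients, and the pralatrexate arm has extra non-PD stopping rules (omitted doses, dosing gaps, two years of treatment) that can also lead to other therapy before PD.

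**Already visible.** The Subsequent Therapy table in SAP Table 9.1 reports timing and response status at the start of that therapy. This is useful disclosure, but it is not a rule for ORR.

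**Conclusion.** The point holds for therapy begun before documented PD, including therapy begun after a site-called PD that central review does not confirm. For those patients the written rule credits responses to transplant, other drugs or crossover pralatrexate to the randomized arm, in either arm, contrary to the endpoint's own definition. That attribution problem follows from the text and needs no assumption.

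The size does rest on assumptions. The rise of 2.6-13.4 points is a one-arm illustration that depends on the assumed share starting new therapy, the assumed true ORR and the assumed denominator. Some offsetting rise in the pralatrexate arm is possible.

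A reader might also infer that the trial's main conclusions are at risk. They are not: ORR lies outside the step-down from PFS to OS, and no stopping decision uses it. The change should be made, but the matter is confined to the secondary endpoint.

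**What to change.** In SAP 8.5.3 and Protocol 15.7.3:

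- Define best overall response as the best central assessment from randomization up to the earlier of documented PD and the start of the first subsequent PTCL therapy. Subsequent therapy here means radiotherapy, systemic therapy including crossover pralatrexate, or transplant.
- State that the separately recorded best response to the first subsequent therapy is not used for ORR.
- Keep the version without the cut-off as a sensitivity analysis.

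Leave the PFS follow-up rule as it is.

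The cost is a sentence or two in each document and a date filter. Subsequent therapies are already collected and their timing is already to be tabulated, so no new data are needed. The downside is that the observed ORR may be slightly lower.
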